- c. Status epilepticus at any time during the clinical investigation.
- d. Any Suicidal Behavior as classified by the Columbia Suicide Severity Rating Scale (C-SSRS) or a "yes" answer to questions 4 and 5 in the Suicidal Ideation section of the C-SSRS. These patients should be referred to psychiatric evaluation immediately.

11. Any subject who has the following liver enzyme findings should be immediately contacted and instructed to stop the study drug or start immediate down titration of the study drug

- a. ALT or AST $> 8 \times$ ULN
- b. ALT or AST $> 5 \times$ ULN for more than 2 weeks
- c. ALT or AST $> 3 \times$ ULN and total bilirubin $> 2 \times$ ULN
- d. ALT or AST $> 3 \times$ ULN with the appearance of fatigue, nausea, vomiting, right upper quadrant pain or tenderness, fever, rash or eosinophilia

Patients with ALT or AST $> 3 \times$ ULN but $\leq 8 \times$ ULN and no clinical signs or symptoms indicating liver dysfunction can, at the discretion of the investigator, continue the intake of study drug with close monitoring.

All patients who fall into either category (patients who must discontinue the study drug [a, b, c, and d] and who may continue the study drug with close monitoring) must be brought back to the study center without any delay, the next day if possible, but no later than 72 hours after the study results have been received, for evaluation of the underlying cause and confirmatory laboratory testing. More frequent monitoring of the liver tests should be initiated.

Discontinuation decisions will be made at each participating site by the Site Principal Investigator. If feasible, the process of discontinuation should be discussed with the Medical Monitor. The decisions regarding the discontinuation of the investigational therapy, whether the study medication should be stopped immediately or tapered should be discussed with the Medical Monitor, but final decisions about the process will remain at the discretion of the Site Principal Investigator.

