		
appearance of fatigue, nausea, vomiting, right upper quadrant pain or tenderness, fever, rash or eosinophilia
 
Patients with ALT or AST .3xULN but <8xULN and no clinical signs or symptoms indicating liver dysfunction can, at the discretion of the investigator, continue the intake of study drug with close monitoring.
 
All patients who fall into either category (patients who must discontinue the study drug [a, b c, and d] and who may continue the study with close monitoring) must be brought back to the study center without any delay, the next day if possible, but no later than 72 hours after the study results have been received, for evaluation of the underlying cause and confirmatory laboratory testing. More frequent monitoring of the liver tests should be initiated.

--	--	--

Reason for Change: Subjects with <35% improvement in seizure frequency as compared to baseline: This criteria is intended to ensure that patients are periodically assessed for benefits and risks of ganaxolone, and that the patients who no longer derive significant benefit from ganaxolone are considered for exclusion. **C-SSRS:** More specific guidance how to utilize the C-SSRS instrument in assessing risk for suicide is provided. Specifically, patients with any suicidal behavior and/or suicidal ideation with intent or plan (ideation questions 4 and 5 in the C-SSRS) should be discontinued from the study and referred to psychiatric evaluation. **Managing elevated LFTs:** These stopping rules are intended to guide the investigator how to manage patients with elevated liver enzymes during the study. These stopping rules are in line with FDA's recommendation on managing patients with elevated liver enzymes during clinical trials (Guidance for Industry: Drug-Induced Liver Injury: Premarketing Clinical Evaluation)

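### Withdrawal criterion 11: the sentence allowing continued dosing, read literally, covers symptom-free patients at >5 to ≤8×ULN for more than 2 weeks, whom 11b tells to stop or down-titrate

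*Protocol*

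**What the plan says.** Criterion 11 in Protocol section 8.3.4.1 has four parts that bear on this point.

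- **The instruction.** A subject with any of the listed liver findings "should be immediately contacted and instructed to stop the study drug or start immediate down titration of the study drug".
- **The findings.** 11a is ALT or AST above 8×ULN. 11b is ALT or AST above 5× "ULN for more than 2 weeks". 11c is ALT or AST above 3×ULN with total bilirubin above 2×ULN. 11d is ALT or AST above 3×ULN with any of a list of symptoms, rash or eosinophilia. 11b carries no symptom condition.
- **The permission.** Patients above 3 and up to 8×ULN with "no clinical signs or symptoms indicating liver dysfunction can, at the discretion of the investigator, continue the intake of study drug with close monitoring".
- **The recall sentence.** It applies to both groups, described as "patients who must discontinue the study drug [a, b, c, and d] and who may continue the study drug with close monitoring". Both must be brought back "no later than 72 hours after the study results have been received, for evaluation of the underlying cause and confirmatory laboratory testing". The next sentence adds: "More frequent monitoring of the liver tests should be initiated".

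The section closes by saying who decides: "Discontinuation decisions will be made at each participating site by the Site Principal Investigator". It asks for discussion of the discontinuation process with the Medical Monitor if feasible. A further sentence, without that qualifier, asks that decisions on discontinuing therapy, including stopping at once versus tapering, be discussed with the Medical Monitor. Final decisions about the process stay with the site.

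**The concern.** The permission is defined by an enzyme range and the absence of signs or symptoms, and by nothing else. It has no duration limit and no exception for patients who meet a–d. 11b is defined by an enzyme level and a duration, whether or not there are symptoms. The two definitions therefore share patients: a mandatory stop and a discretionary permission to continue can both describe the same person.

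The usual route to 11b passes through this overlap. A symptom-free patient found at 6×ULN properly continues under the permission. Once the elevation has lasted more than 2 weeks, 11b applies, but nothing in the permission says that it has ended.

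The study's primary objective is safety and tolerability, and Appendix 7 gives the purpose of the block: "These stopping rules are intended to guide the investigator how to manage patients with elevated liver enzymes during the study". Site investigators apply it, across about 58 planned sites (section 5). Exclusion criterion 3 also sends the Visit 10 laboratory results from Study 1042-0603, which are not available at enrolment, to criterion 11. The wording therefore matters from the entry visit on. A hepatic stopping rule should be unambiguous when that sentence is read alone.

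**Working it through.** The plan gives no figure to reproduce. The check is whether the two definitions can be met together.

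**Notation** (all limits from section 8.3.4.1, criterion 11). Let x be ALT or AST in multiples of ULN, t the time above 5×ULN, and B total bilirubin in multiples of ULN.

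- Permission: 3 < x ≤ 8, no signs or symptoms, any t, any B.
- 11a: x > 8.
- 11b: x > 5 and t > 2 weeks.
- 11c: x > 3 and B > 2.
- 11d: x > 3 with a listed finding.

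**Overlap of each stop criterion with the permission**

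| Criterion | Overlap |
|---|---|
| 11a | None: x > 8 and x ≤ 8 exclude each other |
| 11b | 5 < x ≤ 8, t > 2 weeks, no signs or symptoms |
| 11c | 3 < x ≤ 8, B > 2, only if raised bilirubin alone is not a clinical sign |
| 11d | None, if every 11d finding is taken as a sign or symptom |

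**Worked example.** Take x = 6 for 3 weeks, B = 1.0, no symptoms. 6 > 5 and 3 > 2, so 11b is met. 3 < 6 ≤ 8 without symptoms, so the permission also fits.

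**Grid check.** x = 3.5, 5, 5.5, 7, 8, 8.5; t = 1, 2, 3 weeks; B = 1.0, 2.5; symptoms no or yes. This gives 6 × 3 × 2 × 2 = 72 profiles. Those meeting both the permission and a stop criterion were: 11a 0, 11b 6, 11c 15, 11d 0. Three profiles count under both b and c, so 6 + 15 − 3 = 18 distinct profiles. The 15 for 11c assume that raised bilirubin is not a clinical sign. The counts show where the definitions meet; they are not frequencies.

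**Can the phrase on clinical signs remove the 11b overlap?** Only if raised enzymes are themselves such a sign. Everyone covered by the permission is above 3×ULN, so on that reading it would admit nobody.

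**How much of 11b is affected?** Remove the patients whom another criterion already stops: x > 8 (11a), B > 2 (11c) and any 11d finding. What remains is 5 < x ≤ 8, t > 2 weeks, B ≤ 2 and no 11d finding. That is nearly the same group as the 11b overlap, so the permission literally reaches almost everyone whom 11b alone would stop.

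**After adding the condition that none of a–d is met.** The overlap is empty by construction. The permission then covers symptom-free patients with B ≤ 2 and no 11d finding, at either 3 < x ≤ 5 for any duration or 5 < x ≤ 8 with t ≤ 2 weeks.

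**The case against.** The strongest reply is that the block resolves itself. The recall sentence sorts patients into two groups and lists 11b by letter among those who must discontinue. On that reading 11b is the missing time limit. The permission has to reach 8×ULN to cover the first 2 weeks, after which the patient moves to the other group. The 72-hour recall and more frequent tests supply the data to detect the change.

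Most of this stands. The intended order is clear from the whole block, and a–d are meant to prevail. What does not stand is that no correction is needed. The recall sentence treats the two groups as separate, but the permission does not separate them. The word must appears only in a parenthesis within a sentence about recall. The criterion's own instruction says should, and section 8.3.4.1 opens by listing reasons for which the investigator may discontinue a subject. The precedence has to be inferred.

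It can also be said that the clause leaves investigator latitude where it was, since that opening and the site's decision role are untouched. That is true. The clause removes a contradictory permission and claims nothing more.

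A reader might infer three stronger points that the documents do not support:

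- **That the protocol authorises continued dosing of patients who must stop.** It does not, read as a whole: the recall sentence puts 11b patients in the group that must discontinue.
- **That sites decide with Medical Monitor contact only if feasible.** That qualifier attaches to discussing the process. The next sentence asks, without it, that discontinuation decisions be discussed.
- **That 11c is equally exposed.** The protocol does not define clinical signs, so this overlap is conditional.

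**Conclusion.** The point holds as a minor patient-safety correction to a stopping rule whose wording is internally inconsistent. One of the four stop criteria overlaps the permission for certain: 11b, in the band >5 to ≤8×ULN once it has lasted more than 2 weeks without signs or symptoms. No threshold, duration or monitoring interval is disputed.

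The practical effect is small. Both groups get the same recall and closer liver testing, and no planned analysis changes. Few patients are expected, but the documents do not allow the number to be bounded. Protocol section 6 reports transient elevations above 3×ULN in less than 1% of subjects treated with ganaxolone, but that is programme-wide, over studies lasting from 1 day to more than 2 years. SAP section 9 reports early termination and low patient numbers without giving a count.

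The conclusion rests on reading the permission as written and on raised ALT or AST not itself being a clinical sign, which the sentence's own range requires.

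**What to change.** Make the permission conditional on meeting none of the stop criteria. The sentence would read: Patients with ALT or AST >3×ULN but ≤8×ULN who meet none of a–d and have "no clinical signs or symptoms indicating liver dysfunction can, at the discretion of the investigator, continue the intake of study drug with close monitoring".

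Nothing else in criterion 11 needs to change. The clause also settles the 11c question without a definition of clinical signs. The cost is one clause in one sentence, by amendment or clarification letter, with no added visits, tests or data.

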8.3.4.2 Early Termination Procedures

Any subject who informs the site of an intention to withdraw from the study, or any subjects who are discontinued prior to the end of the study, will be asked to complete the procedures for Visit 7 (Study Completion/Early Term) which include: concomitant AED review, vital signs, physical and neurological exams, laboratory assessments, ECG, pregnancy test, C-SSRS, collection of adverse events, CGI-I, PCGI-I and seizure calendar review. The study drug will then be continuously tapered over one to two weeks, if possible, based on the dose and duration of treatment. A post-taper safety follow-up visit would then be completed. Subjects who are discontinued from the clinical investigation should return to their physician's care and continue appropriate medical treatment. Any AEs that have not resolved as of discontinuation will be followed until resolution. An end-of-study letter will be provided, if requested. Any follow-up information that is available will be added to the case report form up until the time that the database is locked.

8.3.4.3 Consequences of Early Termination

The protocol specifies dose de-escalation of study medication over one to two weeks depending upon dose and duration of treatment. This recommendation is based on cumulative evidence from various classes of CNS drugs that slow taper is beneficial. It is possible that abrupt cessation of the drug might cause discontinuation symptoms. Every effort will be made to ensure implementation of the dose de-escalation.

8.4 TREATMENTS

8.4.1 Identity of Investigational Product(s)

Ganaxolone will be provided in size 00 white/opaque gelatin capsules packaged in HDPE bottles with a foil induction seal and child resistant closure. Each bottle will contain 70 capsules. Each capsule contains 225 mg ganaxolone (3 α -hydroxy-3 β -methyl-5 α -pregnan-20-one), and hydroxypropyl methylcellulose, sucrose, polyethylene glycol 3350, polyethylene glycol 400, sodium lauryl sulfate, sodium benzoate, citric acid anhydrous, sodium methyl paraben, microcrystalline cellulose, 30% Simethicone Emulsion, gelatin capsules, polysorbate 80, and sodium chloride.

All study medication will be stored at the research pharmacy prior to dispensing, or in a locked cabinet accessible only to members of the investigative research team after the completion of each study visit. Study medication should be stored at room temperature 15°C to 25°C (59°F to 77°F).

8.4.2 Treatment Groups

Starting at Visit 1, all subjects will take ganaxolone beginning with the dose currently being taken in the 1042-0603 study, between 900 - 1800 mg/d.

8.4.3 Subject Numbering

Subjects will retain the 6-digit subject number assigned by each site's study staff for preceding protocol 1042-0603. The subject's number and initials (first/middle/last, in regions where permitted) are required to be entered on all clinical investigation documentation (i.e., CRFs, labeling of clinical materials and samples containers, drug accountability logs, etc.).

8.4.4 Selection of Doses in the Study

In meeting efficacy and tolerability criteria to participate in the study, it is expected that the subject will continue with the dose of ganaxolone (between 900-1800 mg/d) last prescribed in Study 1042-0603. Changes at V1 can be addressed with the Sponsor's Medical Monitor. During the study, the dose of ganaxolone may be adjusted at the Investigator's discretion based on tolerability and efficacy between 900 and 1800 mg/d, typically on the MTD of ganaxolone that provides adequate seizure control. Doses may be adjusted upward or downward in 225 mg/d increments every 3 days to reach an optimal dose level over the duration of the 52-week treatment period. Dose adjustments should be made with the investigator's agreement. Frequency of dosing changes may not be less than 3 days unless required for safety.

De-escalation Period: The study drug will be decreased in increments of 450mg/d in 4-day intervals over 12 days for 1800 mg. Decreases from doses less than 1800 mg will be adjusted accordingly (See [Table 2](#)). The subject will return for final post-taper safety assessment visit.

Details of the de-escalation regimen are provided in the table below.

Table 2. Dosing Schedule for De-Escalation Period

De-Escalation, Study Completion or Early Termination (ET)			
Visit	Taper Day	Dose (mg)/day	225 mg cap/day
Visit 7 (Study Completion/Early Term)	Last full dose	1800	8
	1	1350	6
	2	1350	6
	3	1350	6
	4	1350	6
	5	900	4
	6	900	4
	7	900	4
	8	900	4
	9	450	2
	10	450	2
	11	450	2
	12	450	2
	13	0	0
	14	0	0

8.4.5 Dose Administration

Ganaxolone will be administered BID, 12 hours apart with food, i.e. 8:00 AM with breakfast and 8:00 PM after the evening meal. A missed dose of study medication may be taken later up to 8 hours before the next scheduled dose, otherwise the missed dose should not be given (See Section 8.4.6 Missing a Dose). It is important that ganaxolone be dosed with food.

The dose of ganaxolone may be adjusted based upon tolerability or efficacy. Subjects experiencing intolerable AEs at any dose level may have the dose reduced per Investigator direction to attempt to alleviate the event. See [section 8.4.4](#) for dosage adjustments and de-escalation procedures.

8.4.6 Missing a Dose

A missed dose of study medication may be taken up to 8 hours before the next scheduled dose; otherwise, the missed dose should not be given. For example, if a subject usually takes their doses at 7:00 AM and 7:00 PM and forgets to take a 7:00 PM dose at

dinnertime, that dose may be taken up to 9:00 PM at night (2 hrs after the evening meal, more than 8 hours until the next 7:00 AM dose). Alternatively, that dose could be taken until 11:00 PM at night with a small snack.

Subjects should be instructed that if s/he misses 4 doses in a row or more, the site should be contacted to determine whether any adjustment in study medication is needed.

8.4.7 Blinding

This study is not blinded so all subjects will receive active drug. All bottles will be labeled with a unique 6-digit number to help track study drug accountability, lot number, expiry date, and ganaxolone 225 mg capsules.

8.4.8 Excluded, Prior and Concomitant Medications

Subjects participating in the study are to be taking 1-3 AEDs in addition to the investigational medication. AEDs may be adjusted during the course of the study, but subjects must continue on at least one AED. Marketed medications indicated for the treatment of partial seizures are acceptable with the exceptions noted below:

Vigabatrin: Current use of vigabatrin (Sabril) is not permitted.

Ezogabine (retigabine; Potiga; Trobalt): Current use of ezogabine (retigabine) is not permitted.

Perampanel (Fycompa): Perampanel is permitted as a concomitant medication only if the subject has been on a stable dose for at least 3 months prior to Visit 1 and has not experienced any serious psychiatric and behavioral reactions and is expected to remain on a constant dose throughout the study.

Felbamate: Felbamate (Felbatol) is permitted as a concomitant medication only if the subject has been on felbamate for at least 18 months and has stable AST/ALTs and hematology laboratory tests and is expected to remain constant throughout the study.

Benzodiazepines: If a subject is taking a benzodiazepine chronically for epilepsy and/or non-epilepsy conditions, it will be counted as 1 of the 3 AEDs.

Vagal Nerve Stimulator: Subjects receiving treatment with a VNS may be included.

VNS will not be counted as one of the 3 concomitant AEDs.

8.4.9 Excluded Concomitant Medications

A list of medications that are **inducers or inhibitors of CYP 3A4/5/7** and are not permitted during the study are in [Appendix 2](#). Consult with your in-country Medical

Monitor if you have any questions. Note that **phenytoin**, **carbamazepine** and **phenobarbital** are permitted as background AEDs though they are moderate CYP 3A4 inducers. Treatment with the 5- α -reductase inhibitor **finasteride** is not permitted during the study.

Generally, concomitant medications including non-prescription medication can be used if medically necessary for indications that are not exclusionary in the protocol, and if the medication is not expected to interact with study medication nor to adversely impact the subject's ability to comply with protocol requirements (such as keeping seizure calendar and clinic appointments.) The Investigator must make the decision to authorize the use of such a medication only after consideration of the clinical situation, the potential for masking symptoms of a more significant underlying event, and whether the use of the medication will compromise the outcome or validity of the clinical investigation. The Medical Monitor may be consulted for additional input. If medication is required, the name, strength, frequency, and reason for use will be recorded in source documents and name and reason entered in the case report form (CRF).

Benzodiazepines may be used intermittently (i.e., 1 to 2 doses over a 24-hour period) as rescue for the control of seizures. For subjects requiring benzodiazepine rescue more than once per 28-day period, the investigator will determine and document the benefit to the subject for remaining in the trial. If a subject requires use of rescue benzodiazepines 3 times or more during a 28-day period, the Sponsor's Medical Monitor should be consulted regarding the subject's continued participation.

Use of dietary supplements or herbal preparations are permitted if subject has been using them consistently for more than 6 months prior to Visit 1, and does not plan changing the regimen for the duration of the study. Changes may be made during the study at the discretion of the Principal Investigator. Use of St. John's Wort is not permitted (see [Appendix 2](#) for prohibited medications).

As with other AEDs, the concomitant use of ganaxolone and alcohol during the course of the study is not advised. The effects of ganaxolone in combination with alcohol are not known.

Grapefruit and grapefruit juice are strictly prohibited during the clinical trial.

8.4.10 Treatment Compliance

A record of all investigational products dispensed and returned will be maintained at each clinical site. This record will include the date the investigational product is dispensed to a subject, initials of the individual dispensing investigational product, quantity dispensed (by unit), the date investigational product containers are returned from the subject, and the quantity returned. Investigational product and associated accountability forms that are maintained at the clinical site will be present for review by Clinical Investigation Monitors at each monitoring visit.

At each visit all subjects will receive monthly Subject Seizure Calendars. Subjects are to record administration of study drug and background AEDs on the Seizure Calendar. Compliance with study drug treatment will be assessed by inspecting the Subjects' Seizure Calendars and returned supplies with queries as necessary. If the subject is suspected to be non-compliant with study medication or seizure calendar recording, he/she may be discontinued from the study.

8.5 Efficacy and Safety Variables

8.5.1 Efficacy Measurements, Safety Assessments and Schedule of Study Procedures

8.5.1.1 Efficacy Measurements

Efficacy will be assessed using the daily seizure calendar, the Clinician's Global Impression of Improvement, and the Patient/Caregiver Global Impression of Improvement.

